8.2.2. Responder Analysis: Week 16 NPS Score Decrease of ≥1 from Baseline

One of the (co)primary endpoints is the change from baseline in NPS score at Week 16. For this variable, a responder may be defined as a subject whose NPS score at Week 16 decreased from baseline by at least 1.0. If

the subject did not make it to Week 16, or if the subject did not achieve an NPS score reduction ≥ 1 , the subject will be deemed a "Non-responder" (Response='No').

Summary statistics for each treatment group will include the number (n) and percentage (%) of subjects who responded, and an exact confidence interval for the % responders.

A logistic regression will be employed with terms for treatment (3 levels: 1=Placebo, 2=Eto Q8W, 3=Eto Q4W), baseline as a continuous covariate, and stratification factor (asthma comorbidity:1=Yes, 0=No).

Using the logistic regression model, for each comparison of the etokimab groups with the Placebo group, the estimated odds ratio for the etokimab versus placebo odds of response, a 95% Confidence Interval for the odds ratio, and the p-value for that comparison will be displayed in the summary table.

It is expected that treatment with etokimab should lead to a greater odds of response vs. not responding, when compared to the Placebo group. A statistically significantly greater odds ratio for the etokimab vs. placebo group comparison will be taken as evidence of efficacy in favor of etokimab.

8.2.3. Responder Analysis: Week 16 SNOT-22 Score Decrease of ≥ 12 from Baseline

The second co-primary endpoint is the change from baseline in SNOT-22 score at Week 16. For this variable, a responder may be defined as a subject whose SNOT-22 score at Week 16 decreased from baseline by at least 12. This cutoff point is based on the minimal clinically important difference (MCID) value reported by Phillips et al. (2018) and Phillips et al. (2019). If the subject did not make it to Week 16, or if the subject did not achieve an SNOT-22 score reduction \geq 12, the subject will be deemed a "Non-responder" (Response='No').

Summary statistics for each treatment group will include the number (n) and percentage (%) of subjects who responded, and an exact confidence interval for the % responders.

The same logistic regression as the responder analysis for NPS score will be employed for SNOT-22. It is expected that treatment with etokimab should lead to a greater odds of response vs. not responding, when compared to the Placebo group. A statistically significantly greater odds ratio for the etokimab vs. placebo group comparison will be taken as evidence of efficacy in favor of etokimab.

8.2.4. University of Pennsylvania Smell Identification Test (UPSIT)

The University of Pennsylvania Smell Identification Test (UPSIT) is a commercially available test used for smell identification to test the function of an individual's olfactory system. It can be self-administered and uses microencapsulated odorants which are released by scratching standardized odor-impregnated test booklets. This 40-item test will be self-administered by subjects at clinic visits on Day 1 (before injection), Week 8 (before injection) and Week 16/EOT. It usually takes 10-15 minutes.

The test consists of 4 different 10 page booklets, with a total of 40 questions. On each page, there is a different "scratch and sniff" strip which is embedded with a microencapsulated odorant. There is also a four choice multiple choice question on each page. The scents are released using a pencil. After each scent is released, the patient smells the level and detects the odor from the four choices. There is an answer column on the back of the test booklet, and the test is scored out of 40 items.

An UPSIT result is scored out of 40. A higher score indicates better olfaction, and scores of 35-40 indicate normal sense of smell (Doty et al.). A single numeric score is collected in CRF.

Summary statistics for each time point will include n, mean, standard deviation, median, minimum, and maximum, for baseline and the change from baseline.

Each etokimab dosing regimen will be compared to the Placebo group via a MMRM modeling the change from baseline in the UPSIT score at Week 16 as the dependent variable; baseline (Day 1) UPSIT score as a covariate, treatment group (3 levels), stratification factor, treatment by stratification factor, categorical time point (Weeks 4, 8, 12 and 16) and treatment by time interaction as fixed effect factors, and subject as a random effect in the model.

8.3. Exploratory Efficacy Endpoints

8.3.1. Patient Reported Quality of Life Scales

8.3.1.1. Medical Outcomes Study 36-item Short Form (SF-36)

The SF-36 is a generic health survey with 36 items (Ware et al. (1992); Hays et al. (1993)) that measure functional health and well-being from the subject's perspective and will be assessed during clinic visits on Day 1 and Weeks 4, 8, 12, 16 and 24. The 36 questions are grouped into 11 sections of questions in the questionnaire. Some of the sections consist of multiple questions. The 36-item patient-reported questionnaire covers eight health domains: physical functioning (10 items), bodily pain (2 items), role limitations due to physical health problems (4 items), role limitations due to personal or emotional problems (4 items), emotional well-being (5 items), social functioning (2 items), energy/fatigue (4 items), and general health perceptions (5 items).

To specify scoring formulas, the 11 sections of the SF-36 are denoted by Q1 to Q11 according to the order in the questionnaire and the individual items in each question are denoted by their alphabetic order. These may be restated into items 1 to 36 (Please refer to Appendix 19.1).

Scores for each domain range from 0 to 100, with a higher score defining a more favorable health state. The 8 scaled scores are weighted sums of the questions in each section. Scores range from 0 - 100, with lower scores indicating more disability and higher scores indicating less disability. The 8 dimensions/scales are: Physical functioning (PF), Role limitations due to physical health (RP), Role limitations due to emotional problems (RE), Energy/Fatigue (or, Vitality) (VT), Emotional Well-being (or, Mental Health) (MH), Social functioning (SF), Pain (BP), and General Health (GH).

From the eight health dimensions, a physical component summary (PCS), which is the aggregate score of the PF; RP; BP and GH scales, and mental component summary (MCS) which is the aggregate score of the VT; SF; RE and MH scales, measures may be derived. No total score will be derived. (Lins L. et al. (2016)).

Summary statistics for each of the 8 domains and for the PCS and MCS for Day 1, and Weeks 4, 8, 12, 16, and 24 will include n, mean, standard deviation, median, minimum and maximum for baseline, the time of measurement, and the change from baseline.

For the PCS and MCS separately, the change from baseline at Weeks 4, 8, 12 and 16 will be modeled using an MMRM with baseline SF-36 as covariate, treatment group (3 levels), stratification factor, treatment by stratification factor, categorical time point (Weeks 4, 8, 12 and 16) and treatment by time interaction as fixed effect factors, and subject as a random effect. Treatment comparisons will be based on the week 16 least squares means and standard errors. Associated 95% confidence limits for the LS means and the p-value for comparison of each etokimab dose group with the Placebo group will be displayed.

8.3.1.2. European Quality of Life Scale (EQ-5D)

The impact of CRSwNP on the quality of life of the patient will be assessed using the EQ-5D questionnaire. This questionnaire has two components: health state description and evaluation.

In the description part, the EQ-5D-5L health questionnaire is a health-related quality of life instrument with 5 dimensions: mobility, self-care, usual activities, pain/discomfort, and anxiety/depression. Each dimension has 5 possible levels: no problems, slight problems, moderate problems, severe problems and extreme problems.

The summary of results will follow the EQ-5D-5L guidelines for results presentation. For the "Health Profiles" descriptive system summary results will show the number, and proportion (%) of subjects in each Item score (No Problems, Slight Problems, Moderate Problems, Severe Problems, Extreme Problems) by treatment at baseline and at each visit (Weeks 4, 8, 12, and 16).

No formal statistical testing will be carried out for the EQ-5D-5L.

In the evaluation part, the EQ-VAS measures overall self-rated health status on a 0-100 scale, with 0=worst health you can imagine and 100=best health you can imagine. Thus higher scores are suggestive of better health status.

Summary statistics will be presented for the EQ-VAS score showing number of subjects, mean, standard deviation, median, minimum and maximum for each treatment group at baseline and each visit (Weeks 4, 8, 12 and 16), and change from baseline.

An MMRM with the baseline EQ-VAS score as covariate, and treatment (3 levels), stratification factor, treatment by stratification factor, categorical time point (Weeks 4, 8, 12, and 16), and treatment by time interaction as fixed effect factors, and subject as a random effect will be used to obtain least squares estimates for the change from baseline in EQ-5D VAS score in Week 16 for each treatment group. Each etokimab dose group will be compared to the Placebo group using the Week 16 least squares means and standard errors obtained from the model. Associated 95% confidence limits for the LS means and p-values for the treatment comparisons will be displayed.

8.3.1.3. Patient Related Rhinosinusitis Severity Using Visual Analog Scale (VAS)

The Visual Analogue Scale (VAS) for rhinosinusitis is used to evaluate the total severity. The patient is asked to indicate on a continuous scale (VAS) the answer to the question: "How troublesome are your symptoms of rhinosinusitis?" The VAS score ranges from 0 (Not troublesome) to 10 (Worst thinkable troublesome).

The disease severity can be divided into MILD, MODERATE and SEVERE based on total severity visual analogue scale (VAS) score (0 to 10 cm):

- MILD = VAS 0-3
- MODERATE = VAS >3-7
- SEVERE = VAS >7-10

The VAS is administered weekly via an electronic diary device. On Day 1, the eDiary is presented to the subject prior to dosing and the subject must complete the VAS scale before receiving study drug.

The value obtained on Day 1 is the subject's baseline value.

Summary statistics for the VAS for Day 1 and the following weeks until Week 24 will include n, mean, standard deviation, median, minimum and maximum for baseline, the time of measurement, and the change from baseline.

Statistical analysis for the change from baseline in VAS scores at Weeks 4, 8, 12, and 16 will be modeled using an MMRM with baseline VAS score as covariate, and treatment (3 levels), stratification factor, treatment by stratification factor, categorical time (Weeks 4, 8, 12, and 16), and treatment by time interaction as fixed effect factors, and subject as a random effect included in the model. Treatment comparisons will be based on the Week 16 least squares means and standard errors. Associated 95% confidence limits for the LS means and the p-value for comparison of each etokimab dose group with the Placebo group will be displayed.

8.3.1.4. Number of Nocturnal Awakenings

Daily from Day 1 throughout the study, subjects recorded the number of their nocturnal awakenings on the eDiary. Subjects were asked "How many times did you wake up last night." The value obtained on Day 1 will be the subject's baseline value. All other values will be mapped into the weekly analysis visits specified in Section 6.4. Average daily value per each analysis week will be calculated for analysis. Only subjects with a value recorded more than 4 days per week will be included in the analysis.

Summary statistics including mean, standard deviation, median, minimum and maximum at each time point will be provided.

8.3.2. Lund-Mackay Scores

Computed tomography of the sinuses is performed at the clinic on Day 1 and at EOT (Week 16). The Day 1 CT is collected prior to dosing on Day 1. As indicated in the protocol, if necessary, the Day 1 CT can be collected prior to Day 1, however all efforts should be made to conduct CT after subject screening labs have been reviewed and it is determined that the subject is likely eligible for the study. CTs collected within 3 months prior to randomization (Day 1) can be used in lieu of a new Day 1 CT if the necessary imaging requirements are present.

The Lund-Mackay (L-M) scoring system is based on localization with points given for degree of opacification: 0 = normal, 1 = partial opacification, 2 = total opacification. These points are then applied to the maxillary, anterior ethmoid, posterior ethmoid, sphenoid, and frontal sinus on each side. The osteomeatal complex is graded as 0 = not occluded, or 2 = occluded deriving a maximum score of 12 per side (Lund and MacKay, 1993). For patients in whom the osteomeatal complex (OC) is missing (because of a previous surgery) the reader should consider the location of the former OC and provide a scoring (as if the OC was there). An aplastic

(absent) frontal sinus receives a score of 0. Thus, a combined L-M score of up to 24 is possible. The table below summarizes the scoring system:

Sinus	Right sinus	Left sinus
Frontal	0, 1, 2	0, 1, 2
Anterior ethmoids	0, 1, 2	0, 1, 2
Posterior ethmoids	0, 1, 2	0, 1, 2
Maxillary	0, 1, 2	0, 1, 2
Sphenoid	0, 1, 2	0, 1, 2
Ostiomeatal complex	0, 2	0, 2
Total score for each side	0-12	0-12

For the sinuses: 0=normal; 1=partial opacification; 2=total opacification.

For the ostiomeatal complex: 0=not occluded; 2=occluded

The L-M total score is obtained by summing the scores for the right and left sinuses. For simplicity, we will refer to the total score as the L-M score. Higher values for the L-M scores indicate more opacification.

Baseline L-M score will be defined as the L-M score obtained on Day 1, or the last available L-M score prior to treatment on Day 1. The L-M score at Week 16/EOT will be defined as the last value available during the treatment period.

Summary statistics will include n, mean, standard deviation, median, minimum, and maximum, and the percent change from baseline. A Wilcoxon signed ranks test p-value for the within treatment group percent change from baseline will be displayed.

Each etokimab dosing regimen will be compared to the Placebo group via an analysis of covariance (ANCOVA) modeling the percent change from baseline in L-M score at Week 16/EOT using the baseline L-M score as a covariate, with treatment (3 levels) as a factor. Least squares adjusted means from the ANCOVA model will be used to perform pairwise comparisons of each etokimab dosing regimen with the Placebo group. An estimate of treatment difference and accompanying 95% confidence intervals will be produced from the model. Each (two-sided) comparison of an etokimab dose group with the Placebo group with respect to L-M scores will use the 5% level of significance.

8.3.3. Nasal Peak Inspiratory Flow (NPIF) (AM and PM)

Nasal Peak Inspiratory Flow (NPIF) will be used to evaluate nasal flow through the nose. At screening (Visit 1), subjects will be issued an NPIF meter for recording morning (AM) and evening (PM) NPIF. Subjects will record values (L/min) twice a day for 7 consecutive days during screening period, and twice a day, every day throughout the treatment and safety follow-up period (Week 0-24), according to diary instructions. Subjects will be instructed on the use of the meter, and written instructions on the use of the NPIF meter will be provided to the subjects. In addition, the investigator will instruct the subjects on how to record the following variables in the diary on a daily basis.

- AM NPIF should be performed approximately 15 minutes after arising prior to taking MFNS
- PM NPIF should be performed in the evening prior to taking MFNS

Three NPIF efforts will be made by the subject and recorded. All 3 values will be recorded by the subject in the diary, and the highest value will be used for evaluation. The procedure takes about 5 minutes.

Baseline AM (PM) NPIF will be the mean AM (PM) measurement recorded for 7 consecutive days or 1 week during the screening period, prior to the first dose of investigational product. Subjects should complete the diary twice a day for 7 consecutive days during the screening window, however at least, 5 of the 7 days must be completed during the screening period to be eligible for enrollment.

During the screening period NPIF recordings are collected on paper diary provided to subjects. Starting from Day 1, subjects are provided an eDiary to collect NPIF recordings throughout the remainder of the trial. Diary compliance must be approximately 80% throughout the study duration. For both the paper diary utilized during the screening period and the eDiary during the treatment period, the NPIF meter is set up only to allow for a value equal to or greater than 30, so the lowest NPIF value a subject can record is set at 30.

NPIF (AM and PM) means will be calculated for each week only for the subjects who have greater than 50% of diary compliance for that specific week:

Summary statistics for each month will include n, mean, standard deviation, median, minimum and maximum, and the change from baseline. For each treatment arm, a Wilcoxon signed ranks test will be used to assess whether the change from baseline is statistically significant.

The etokimab dose groups will be compared to the Placebo group during the treatment period (up to Week 16) only. The values obtained between Week 17 and Week 24will not be included in the efficacy analysis, as follow-up is intended for safety only.

Statistical analysis of morning/evening NPIF during the treatment period will employ an MMRM, where the change from baseline in Weeks 4, 8, 12 and 16 AM (PM) NPIF values are modeled using the baseline value as a covariate; treatment (3 levels), stratification factor, treatment by stratification factor, categorical time (Weeks 4, 8, 12 and 16), and treatment by time interaction as fixed effect factors; and subject (the repeated measures) as random effect. The analysis is similar to that performed for the NPS and SNOT-22 scores.

The primary time point for the analysis of morning/evening NPIF is Week 16. The Week 16 least squares adjusted means from the MMRM will be used to perform pairwise comparisons of each etokimab dosing regimen with the Placebo group. An estimate of treatment difference and accompanying 95% confidence intervals will be produced from the model. It is expected that treatment with etokimab will lead to higher AM/PM NPIF values at Week 16 than obtained at baseline. A statistically significant difference (P<0.05) where the least squares means for the etokimab group is higher than for the Placebo group will be regarded as evidence of efficacy for etokimab compared to Placebo.

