To assess improvement in Quality of Life (QoL) in subjects with CRSwNP treated with etokimab compared to placebo following a 16-week treatment period	 QoL: 36-item Short Form Health Survey (SF-36) European QoL scale (EQ-5D) Patient-related rhinosinusitis symptoms severity using a visual analogue scale (VAS) Number of nocturnal awakenings 	To assess the effect of etokimab on the patients' symptoms and quality of life
To assess other effects of etokimab compared to placebo in subjects with CRSwNP following a 16-week treatment period	 Percent change from baseline to Week 16 in sinus opacification as assessed by CT scan using Lund-Mackay score Change from baseline to Week 16 in nasal peak inspiratory flow (NPIF) Change from baseline to Week 16 in NPS in subjects with comorbid asthma Change from baseline to Week 16 in Sino-Nasal Outcome Test (SNOT-22) scores in subjects with comorbid asthma Percent change from baseline to Week 16 in 3-dimensional volumetric measurement of the maxillary sinus as assessed by CT scan Change from baseline to Week 16 in forced expiratory volume (FEV₁) (overall and in subgroup with asthma) Change from baseline to Week 16 in FEV₁ percent of predicted (overall and in subgroup with asthma) 7-Item Asthma Control Questionnaire (ACQ-7) in asthma subgroup Reduction of eosinophils (blood eosinophil count) from baseline (Day 1 pre-dose) to Week 16 	All other efficacy endpoints have been recategorized as exploratory endpoints Additional measures of treatment response are established methods to characterize the clinical impact of treatment Patient-reported outcomes specific to CRSwNP provide additional evidence to support the physician assessment of outcome

OBJECTIVES	ENDPOINTS	JUSTIFICATION FOR ENDPOINTS
	 Time to study treatment discontinuation Incidence of treatment discontinuation due to need for oral corticosteroids (OCS) or nasal polyp surgery Change in Nasal Polyp Resource Questionnaire from baseline to Week 16 	

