6. GENERAL ASPECTS FOR STATISTICAL ANALYSIS

6.1. General Methods

The following conventions will be utilized in the analyses:

- The final statistical analysis will not be performed until all the reportable data have been collected, queries answered, and the database locked.
- All relevant individual subject data will be provided in data listings sorted by treatment arm and subject number. The following treatment group labels will be used: "Placebo", "etokimab Q8W", and "etokimab Q4W". Where subjects who were not randomized are included in listings, the treatment arm will be indicated as "Not Assigned" or "Not Randomized".
- Tabulations will be produced for appropriate demographic, baseline, efficacy and safety parameters. All tabular summaries will be presented by treatment arm as indicated above. A total column may be included under "All Subjects" where necessary or appropriate.
- In general, continuous variables will be summarized by descriptive statistics including the number of observations (n), mean, standard deviation (SD) or standard error (SE), median, minimum (min), and maximum (max); the lower (Q₁) and upper quartile (Q₃) may be included in some summaries if deemed necessary or important. The same number of decimal places as the raw data will be presented when reporting min and max, 1 more decimal place than in the raw data will be presented when reporting mean, median, lower and upper quartiles and 2 more decimal places than in the raw data will be presented when reporting SD or SE.
- Categorical data will be summarized using the number of observations (n), frequency, and percentage of subjects in the relevant analysis set and treatment group falling within each category.
- Unless otherwise specified, where there are multiple measurements at a post-baseline visit or time of assessment, the value closest to the target date within the specified window for the assessment visit will be used for analysis.
- For numerical variables, change from baseline will be calculated as the value of interest at the time of measurement minus the corresponding baseline value.
- All statistical tests will be two-sided; unless otherwise indicated; two-sided p-values < 0.05 will be regarded as statistically significant, and confidence intervals (CI) will be 2-sided and have 95% confidence level.
- All subject data will be included in listings.
- Data analyses will be conducted using validated computer software (e.g. SAS[®] Version 9.4 or higher).

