8.3.5. Change in the Percentage of Volumetric Maxillary Sinus Occupied by Disease (VMSOD)

At clinic visits on Day 1 and Week 16/EOT, computed tomography (CT) scans are used to calculate the volume of the air (mL), the volume of the mucosa (mL), the % occupied by disease, and the thickness of the lateral wall. Central reading before Day 1 (Visit 2) will be used for comparison with the EOT reading. The sites will remove subject-identifying information from the imaging data header prior to sending the imaging data to the central reader.

The percentage occupied by disease will be analyzed. Baseline is defined as the percentage of VMSODs on Day 1. The Week 16/EOT value is the % of VMSOD at the Week 16/EOT assessment. For each subject, the difference in the % VMSOD between the Week 16/EOT and baseline values will be calculated (EOT value minus baseline value) as a measure for the percent change in opacification.

Summary statistics for % of VMSOD for baseline value, Week 16/EOT value, and the change from baseline (Week 16/EOT minus baseline) will include n, mean, standard deviation, median, minimum, and maximum. For each treatment arm, a Wilcoxon signed ranks test will be used to assess whether the change from baseline is statistically significant.

Statistical analysis of the change in % VMSOD from baseline at Week 16/EOT will be performed using ANCOVA with baseline % VMSOD as a continuous covariate, and treatment (3 levels) as a factor. Gender (M/F) may be considered for inclusion in the model. If preliminary analysis shows the gender-by-treatment interaction term to be not significant at alpha=0.05, the gender-by-treatment term will be dropped out of the model. The final model may include main effect for gender if this is deemed important to adjust for.

Least squares adjusted means from the final ANCOVA model will be used to perform pairwise comparisons of each etokimab dosing regimen with the Placebo group. An estimate of treatment difference and accompanying 95% confidence intervals will be produced from the model.

Each (two-sided) comparison of an etokimab dose group with the Placebo group with respect to % VMSOD will use the 5% level of significance. It is expected that treatment with etokimab will lead to lower % VMSOD values at week 16/EOT than observed at baseline. A statistically significantly higher adjusted mean score for an etokimab group compared to the Placebo group will be regarded as evidence of efficacy for etokimab compared to Placebo.

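### SAP 8.3.3 and 8.3.5 attach an efficacy rule to six unadjusted, ungated exploratory tests: about a 9–13% chance of a false signal, against 2.5% for one directional test

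*SAP*

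**What the plan says.** **NPIF (SAP 8.3.3).** Morning and evening values are each analysed by MMRM, and "The primary time point for the analysis of morning/evening NPIF is Week 16". The Week 16 means are used to "perform pairwise comparisons of each etokimab dosing regimen with the Placebo group". The section then gives a reading rule at the 5% level: a significant result "where the least squares means for the etokimab group is higher than for the Placebo group will be regarded as evidence of efficacy".

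**%VMSOD (SAP 8.3.5).** Each regimen is compared with placebo by ANCOVA, two-sided at 5%. A significant difference in a stated direction "will be regarded as evidence of efficacy for etokimab compared to Placebo".

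**Lund-Mackay (SAP 8.3.2).** A level is set but no efficacy rule: "Each (two-sided) comparison of an etokimab dose group with the Placebo group with respect to L-M scores will use the 5% level of significance".

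**General convention (SAP 6.1).** Unless otherwise indicated, "two-sided p-values < 0.05 will be regarded as statistically significant".

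**Status.** Protocol Section 3 lists NPIF and the CT volume measure as exploratory and notes: "All other efficacy endpoints have been recategorized as exploratory endpoints". Protocol Table 3 gives only the models for these endpoints, with no rule for reading the result. Among the changes from the protocol, SAP Section 12 lists only nocturnal awakenings.

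**The controlled part (SAP 8.1 and 8.2).** Both co-primaries must reach p<0.05, with Q4W tested before Q8W. Only then are the four secondaries tested, in fixed order, first for Q4W and then for Q8W. After the first p≥0.05, later secondaries are not interpreted for significance.

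**The concern.** SAP 8.2.1 to 8.2.3 use almost the same evidence-of-efficacy language for three of the secondaries, but there SAP 8.2 switches it off once the hierarchy fails. Nothing switches it off in 8.3.3 or 8.3.5. Endpoints ranked below the secondaries therefore get the same inferential wording with less protection.

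If both co-primaries failed, a report could still cite a prespecified rule and state evidence of efficacy from one favourable result among six: AM NPIF, PM NPIF and %VMSOD, each in two arms.

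The two sections also stand apart from the rest of 8.3. For the SF-36 summaries and the rhinosinusitis VAS, p-values are only displayed. For the EQ-5D-5L profile, formal testing is ruled out. For most resource-use items, formal inference is ruled out. Neutral wording was therefore available.

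**Working it through.** The plan states no error rate for the exploratory endpoints, so there is no figure of its own to reproduce on this point. The power statements in SAP 3.6 do reproduce (t-test at 27 per arm: 87.8% against the stated 87% for NPS, 92.5% against 92% for SNOT-22), but they do not bear on it.

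**Inputs from the documents**
- Tests carrying an efficacy rule: AM NPIF, PM NPIF and %VMSOD, each for two regimens. 3 × 2 = 6, of which 2 × 2 = 4 are NPIF.
- Time point: Week 16 only, so there is no extra multiplicity over visits.
- Rule per test: a two-sided p<0.05 and a direction. For NPIF it is "A statistically significant difference (P<0.05) where the least squares means for the etokimab group is higher than for the Placebo group". Under the null each test meets its rule with probability 0.05/2 = 2.5%.
- Allocation 1:1:1 with one placebo arm. With equal n and SD, the two contrasts share the placebo variance: correlation = (σ²/n)/(2σ²/n) = 0.5.

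**Inputs assumed.** The documents give no endpoint correlations. Ranges tried: AM with PM NPIF, 0 to 0.95; NPIF with %VMSOD, 0 to 0.5, oriented so that positive means both improve together.

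**Reference if all tests were independent**
- Six tests: 1 − 0.975⁶ = 14.1%
- Four NPIF tests: 1 − 0.975⁴ = 9.6%

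**With correlation.** Six z-statistics were drawn from a multivariate normal with mean zero (no effect in either arm). The covariance was the Kronecker product of the arm matrix (off-diagonal 0.5) and the endpoint matrix. There were 2,000,000 draws, counting any z above 1.96 in the rule's direction. SAP 8.3.5 as written counts a higher %VMSOD mean, although the same section expects lower values. That is a separate matter, so both directions are shown.

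| AM–PM corr. | NPIF–%VMSOD corr. | Six tests, %VMSOD lower counts | Six tests, %VMSOD higher counts (as written) | Four NPIF tests |
|---|---|---|---|---|
| 0 | 0 | 13.0% | 13.0% | 8.9% |
| 0 | 0.5 | 11.6% | 13.4% | 8.9% |
| 0.5 | 0.3 | 11.7% | 12.5% | 8.1% |
| 0.8 | 0 | 11.2% | 11.2% | 7.0% |
| 0.9 | 0.3 | 10.1% | 10.7% | 6.3% |
| 0.95 | 0.5 | 9.2% | 10.3% | 5.8% |

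**Size.** For six tests the rate is about 9–13% (about 10–13% with the %VMSOD direction as written). Against 2.5% for one directional test, 9.2/2.5 = 3.7 and 13.0/2.5 = 5.2. For NPIF alone it is about 6–9%: 5.8/2.5 = 2.3 and 8.9/2.5 = 3.6.

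**The case against.** The case against is substantial, and much of it stands.

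- **Trial-level inference is untouched.** Co-primary success needs both p-values below 0.05 and the secondaries follow in fixed order. No exploratory result spends alpha or changes that conclusion. This stands.
- **Unadjusted exploratory testing is ordinary in Phase 2, and the protocol provides for it.** Protocol 9.4.1 sets two-sided 5% for formal tests unless otherwise specified, and Table 3 names the exploratory analyses. This stands for the testing and for the 5% level. It does not cover the added sentence on what a significant result means.
- **AM and PM NPIF are close to one measurement.** The same subject uses the same meter on the same days, so a high correlation is plausible and NPIF alone may sit near 6%. This stands as a reason to read the lower end of the range.
- **As written, the %VMSOD rule rewards a higher value.** Only the NPIF rules therefore work in the beneficial direction today. This is fair, and it is why the NPIF figure is given separately.

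Three stronger readings are tempting and are not supported:

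- **That any p<0.05 counts, in either direction.** That would give about 18–25% for six tests (26.5% if independent, 1 − 0.95⁶). Both sections require a direction, so this is not the SAP's rule.
- **That the whole of Section 8.3 forms one large family of efficacy claims.** The other analyses set a level or present comparisons and p-values. None carries an efficacy sentence.
- **That the SAP contradicts the protocol outright.** Protocol Section 3 labels the endpoints exploratory. No current protocol text says that only the hierarchy may support a statement about efficacy.

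**Conclusion.** The point holds as a defect of interpretation wording. Two exploratory sections declare in advance that one favourable unadjusted p-value, in either arm and whatever the co-primaries show, is evidence of efficacy. The exploratory heading does not neutralise a sentence that says so explicitly.

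The chance of at least one false signal exceeded 5% at every correlation tried, for the six tests and for NPIF alone. The range depends on the assumed endpoint correlations, on the 0.5 between-arm correlation from equal allocation, and on no effect anywhere. A reader should not infer any inflation of the co-primary or secondary error rate: there is none.

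**What to change.** 1. Delete the sentence in SAP 8.3.3 and the sentence in SAP 8.3.5 that turn a significant difference into evidence of efficacy. In 8.3.5 this also removes the sentence with the reversed direction.
2. Add at the head of SAP 8.3: *Exploratory endpoints are outside the testing hierarchy; estimates and 95% CIs are reported, p-values are nominal and will not be used to conclude efficacy, whatever the co-primary result.*

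The 5% wording in 8.3.2 and 8.3.5 can stay, since it follows Protocol 9.4.1. SAP 6.1 can also stay: its convention yields where the SAP indicates otherwise, and the new sentence does that for 8.3.

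The cost is SAP wording only, with no change to models, data or sample size. The downside is that no exploratory result can then be reported on its own as evidence of efficacy.
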